7.9 Prescription and Normal Tissue Constraints

7.91 For treatment planning, setup uncertainty analyses of 3-5mm perturbations along each translation axis and 3% beam range uncertainty will be performed on the CTV and organs at risk. All CTV target volume parameters must be met under each setup uncertainty analysis. Acceptability of the level of robustness achieved of normal tissue constraints with proton planning will be left to the discretion of the treating physician, provided that all criteria below are met on the planning CT, but will be reported.

7.92 Normal Structures (Note: “of prescription” refers to the non-boost prescription)

Arms 1 and 2

Chest wall and Regional Node CTV

- Per protocol $\geq 95\%$ will receive $\geq 95\%$ of prescription; Variation Acceptable $\geq 90\%$ receives $\geq 90\%$ of prescription
- Per protocol $D_{01cc} \leq 110\%$; Variation Acceptable $D_{01cc} \leq 115\%$

Normal Structures (Note: “of prescription” refers to the non-boost prescription)

Chest wall skin

- Per protocol $D_{1cc} \leq 96\%$ of prescription; Variation acceptable $D_{1cc} \leq 105\%$ of prescription

Supraclavicular skin

- Per protocol $D_{1cc} \leq 80\%$ of prescription; Variation acceptable $D_{1cc} \leq 90\%$ of prescription

Internal mammary nodes

- Per protocol 95% receives 90% of prescription; Variation Acceptable 90% receives 85% of prescription.

Heart (for left-sided cases only)

- Per protocol mean heart dose \leq 1.5% of prescription and; Variation acceptable \leq 3% of prescription

Heart (for right-sided cases only)

- Per protocol mean heart dose \leq 1.5% of prescription; Variation acceptable \leq 2% of prescription

LAD (for left-sided cases only)

- Per protocol D0.01cc \leq 6% of prescription; Variation acceptable D0.01cc \leq 30% of prescription.

RCA (for right-sided cases only)

- Per protocol D0.01cc \leq 6% of prescription; Variation acceptable D0.01cc \leq 30% of prescription.

Ipsilateral lung

- Per protocol V40% \leq 15% (\leq 15% of the ipsilateral lung can receive \geq 40% of prescription); Variation acceptable V40% \leq 20%
- Ipsilateral lung mean dose, V20%, V60%, V80%, and V100% should be recorded

Contralateral lung

- Per protocol V10% \leq 10% (\leq 10% of the contralateral lung receives \geq 10% of prescription); Variation acceptable V10% \leq 15%

Total lung

- Record total lung V20%, V20Gy, and mean dose

Esophagus

- Per protocol proton D1cc \leq 72% of prescription; Variation acceptable D1cc \leq 90% of prescription

Cord

- Per protocol D0.01cc \leq 80%

Brachial Plexus

- Per protocol D0.01cc \leq 102%
Variation acceptable \leq 108%

7.10 Quality Assurance Documentation

7.10.1 At a minimum, the first treatment plan per physician will be centrally reviewed by the principal investigator or designee prior to the start of treatment.

8.0 Radiotherapy Dose Modifications Based on Adverse Events

This study has no pre-specified interruptions due to adverse events. Treatment interruptions are discouraged. If radiation needs to be interrupted for $>$ 2 days, this should be approved by the principal investigator or representative and documented.

9.0 Ancillary Treatment/Supportive Care

Skin changes are common complications of breast cancer radiation therapy. Usual care will be provided as per the treating institution's standard of practice. Mepitel film is allowed. If the skin becomes erythematous and/or there is pruritis, topical steroid cream may be prescribed. The addition of antihistamines may be used for severe pruritis. Patients experiencing pain will be prescribed pain medication.

10.0 Adverse Event (AE) Reporting and Monitoring

10.1 Definitions

Adverse Event- An untoward or undesirable experience associated with the use of a medical product (i.e. drug, device, biologic) in a patient or research subject.

Serious Adverse Event - Adverse events are classified as serious or non-serious. Serious problems/events can be well defined and include;

- death
- life threatening adverse experience
- hospitalization
- inpatient, new, or prolonged; disability/incapacity
- persistent or significant birth defect/anomaly

and/or per protocol may be problems/events that in the opinion of the sponsor-investigator may have adversely affected the rights, safety, or welfare of the subjects or others, or substantially compromised the research data. All adverse events that do not meet any of the criteria for serious, should be regarded as **non-serious adverse events**.

Unanticipated Problems Involving Risks to Subjects or Others (UPIRTSO)- Any unanticipated problem or adverse event that meets the following three criteria:

Serious: Serious problems or events that results in significant harm, (which may be physical, psychological, financial, social, economic, or legal) or increased risk for the subject or others (including individuals who are not research subjects). These include: (1) death; (2) life threatening adverse experience; (3) hospitalization - inpatient, new, or prolonged; (4) disability/incapacity - persistent or significant; (5) birth defect/anomaly; (6) breach of confidentiality and (7) other problems, events, or new information (i.e. publications, DSMB reports, interim findings, product labeling change) that in the opinion of the local investigator may adversely affect the rights, safety, or welfare of the subjects or others, or substantially compromise the research data, **AND**

Unanticipated: (i.e. unexpected) problems or events are those that are not already described as potential risks in the protocol, consent document, not listed in the Investigator's Brochure, or not part of an underlying disease. A problem or event is "unanticipated" when it was unforeseeable at the time of its occurrence. A problem or event is "unanticipated" when it occurs at an increased frequency or at an increased severity than expected, **AND**

Related: A problem or event is "related" if it is possibly related to the research procedures.

Preexisting Condition- A preexisting condition is one that is present at the start of the study. A preexisting condition should be recorded as an adverse event if the frequency, intensity, or the character of the condition worsens during the study period. At screening, any clinically significant abnormality should be recorded as a preexisting condition. At

the end of the study, any new clinically significant findings/abnormalities that meet the definition of an adverse event must also be recorded and documented as an adverse event.

10.2 Recording Adverse Events

CTCAE term (AE description) and grade: The descriptions and grading scales found in the revised NCI Common Terminology Criteria for Adverse Events (CTCAE) version 4.0 will be utilized for AE reporting unless as otherwise stated in the table below.

All appropriate treatment areas should have access to a copy of the CTCAE version 4.0. A copy of the CTCAE version 4.0 can be downloaded from the CTEP web site:

[REDACTED]

10.21 Adverse event monitoring and reporting is a routine part of every clinical trial. First, identify and grade the severity of the event using the CTCAE version 4.0. Next, determine whether the event is expected or unexpected and if the adverse event is related to the medical treatment or procedure. With this information, determine whether the event must be reported as an expedited report (see Section 10.3).

10.22 Assessment of Attribution

When assessing whether an adverse event is related to a medical treatment or procedure, the following attribution categories are utilized:

Definite - The adverse event is clearly related to the agent(s).

Probable - The adverse event is likely related to the agent(s).

Possible - The adverse event may be related to the agent(s).

Unlikely - The adverse event is doubtfully related to the agent(s).

Unrelated - The adverse event is clearly NOT related to the agent(s).

Events determined to be possibly, probably or definitely attributed to a medical treatment suggest there is evidence to indicate a causal relationship between the drug and the adverse event.

10.3 Reporting of Serious Adverse Events and Unanticipated Problems

When an adverse event has been identified, the study team will take appropriated action necessary to protect the study participant and then complete the Study Adverse Event Worksheet and log. The sponsor-investigator will evaluate the event and determine the necessary follow-up and reporting required.

- a. Serious Adverse Events will be reported as part of regular adverse event reporting mechanisms via the data capture system and logged for review reporting.

10.31 Investigator Reporting: Notifying the Mayo IRB:

The IRB requirements reflect the guidance documents released by the Office of Human Research Protections (OHRP), and the Food and Drug Administration (FDA) in early 2007 and are respectively entitled “Guidance on Reviewing and

Reporting Unanticipated Problems Involving Risks to Subjects or Others and Adverse Events” and “Guidance for Clinical Investigators, Sponsors, and IRBs: Adverse Event Reporting – Improving Human Subject Protection.”

10.311 According to Mayo IRB Policy any serious adverse event (SAE) which the Principal Investigator has determined to be a UPIRTSO must be reported to the Mayo IRB as soon as possible but no later than 5 working days after the investigator first learns of the problem/event.

10.312 Non-UPIRTSO – the investigator reports problems or events that do NOT meet criteria of an UPIRTSO in summary format at the time of the next continuing review. The investigator monitors the severity and frequency of subsequent non-UPIRTSOs.

Consider the following information to collect when developing any forms for documentation of adverse events.

Example

Information collected on the adverse event worksheet (and entered in the research database):

- Subject’s name:
- Medical record number:
- Disease/histology (if applicable):
- The date the adverse event occurred:
- Description of the adverse event:
- Relationship of the adverse event to the research (drug, procedure, or intervention):
- If the adverse event was expected:
- The severity of the adverse event: (use a table to define severity scale 1-5)
- If any intervention was necessary:
- Resolution: (was the incident resolved spontaneously, or after discontinuing treatment)
- Date of Resolution:

The investigator will review all adverse event reports to determine if specific reports need to be made to the IRB and FDA. The investigator will sign and date the adverse event report when it is reviewed. For this protocol, only directly related SAEs/UPIRTSOs will be reported to the IRB.

10.4 Adverse events to be graded at each evaluation and pretreatment symptoms/conditions to be evaluated at baseline per the CTCAE v4.0 grading unless otherwise stated in the table below:

System Organ Class (SOC)	Adverse event/Symptoms	Baseline	Each evaluation	Grading scale (if not CTCAE)
Skin and Subcutaneous tissue disorders	Dermatitis Radiation	X	X	CTCAE
	Telangiectasia	X	X	See 10.41

	Breast Edema = CTCAE Vascular Lymphedema	X	X	CTCAE, BCTOS ¹
	Superficial soft tissue Fibrosis	X	X	CTCAE
	Seroma Formation	X	X	CTCAE
	Skin hyperpigmentation	X	X	CTCAE
	Skin hypopigmentation	X	X	CTCAE
Gastrointestinal Disorders	Esophagitis	X	X	
Infections and infestations	Breast infection	X	X	CTCAE
Respiratory, thoracic and mediastinal disorders	Pneumonitis	X	X	CTCAE
General disorders and administration site conditions	Non-cardiac chest pain	X	X	CTCAE

1. BCTOS = Breast Cancer Treatment Outcomes Scale

10.41 Grading Scale for other toxicities

Telangiectasia: Grade 0 – None; Grade 1 – 1cm²; Grade 2 – 2-4cm²; Grade 3 - >4cm²

10.5 Submit via appropriate *reporting mechanisms* the following AEs experienced by a patient and not specified in Section 10.4:

10.52 Grade 3 and 4 AEs regardless of attribution to the study treatment or procedure.

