4.0 Test Schedule

Assessments, tests and procedures	Treatment			Observation ⁷
	Baseline ²	Last day of treatment (+/- 2 days)	12 weeks (+/- 8 weeks) post-radiation	12 months (+/- 3 month) post completion of radiotherapy, 24 months (+/- 3 months), 36 months (+/- 3 months), and at 5 years (+/- 3 months)
History and Physical exam (including breast assessment/exam) ¹	X	X	X	X
Mammogram	X ¹⁰			X ¹¹
Cosmesis ,QOL Outcome Assessment and Breast-Q ¹⁶ (see section 11.3 and Appendix)	X ¹³	X	X	X
Digital Photograph	X	X	X	X
Review of surgical specimen(s) to confirm eligibility	X ³			
Echocardiography ^{9, 14}	X ¹³			X ⁸
Radiation toxicity assessment (see section 10.4)	X	X	X	X
Serum pregnancy test	X ⁴			
Blood specimen ^{5, 17, R}	X ¹⁵	X	X	X ¹²
Surgical tumor specimen ^{6, 18, R}	X			

1. A general history & physical must be done \leq 8 weeks prior to registration. This should include an assessment of ECOG performance status (see Appendix I).

2. Following definitive surgical resection and adjuvant chemotherapy if indicated, prior to the start of radiation.
3. Outside pathology must be reviewed at the treating institution.
4. For women of childbearing potential only, must be within 7 days of radiotherapy
5. See section 14 for collection time and preparation of samples
6. See section 17 for collection time and preparation of samples
7. Patients that cannot come back to Mayo Rochester within the time constraints of the follow-up schedule; efforts to obtain outside records and send QOL's to be completed will occur, however the required items may not be captured.
8. Ideally 6-12 months post radiotherapy in HER2 positive patients treated with HER2 directed therapy and in patients treated with anthracycline as part of routine clinical care. Only followed for Echos 1 year post therapy.
9. Co-enrollment on IRB 15-007443 (echo protocol) is required in Rochester while open
10. Completed \leq 12 months prior to study entry
11. As clinically indicated
12. At 12 months post-treatment visit only to coincide with echocardiography.
13. Should be \geq 14 days since last chemotherapy
14. After closure of IRB 15-007443 (echo protocol) echocardiography tests will be performed only in left sided patients previously treated with anthracycline and/or HER2 directed systemic therapy. This correlative component will occur at Rochester Mayo only.
15. Baseline blood collection will be drawn through co-enrollment on IRB 15-000136 (Radiation Oncology Outcomes Registry and Biobanking Study).

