16.0 Statistical Considerations and Methodology

This is an open label phase II randomized controlled trial to determine the safety of 15 fraction vs 25 fraction scanning beam proton radiotherapy after mastectomy in patients requiring regional nodal irradiation.

16.1 Primary Endpoint:

16.1.2 Primary endpoint: 24 month complicate rate, defined as the percentage of women randomized who develop one or more of the following events:

- 1) grade 3 or higher late adverse events
- 2) unplanned surgical intervention (not including planned serial fat grafting) in patients who undergo mastectomy with reconstruction.

16.2 Secondary Study Endpoints: The secondary aims of this study are to characterize acute and late adverse events including grade ≥ 2 pneumonitis and reconstruction failure rate, assess patient self-reported cosmesis, evaluate fatigue, breast pain, arm function and other patient reported outcomes, compare the locoregional control, disease free, overall survival. Blood will be collected for future studies exploring dose volume and genomic predictors of adverse cosmesis and biomarkers of cardiotoxicity.

The following definitions are used for the secondary endpoints of interest:

- *Acute adverse events* (up to 90 days post-RT): any adverse event, regardless of attribution, that occurs in the first 90 days post-RT.
- *Late adverse events* (up to 5 years post XRT): any adverse event that occurred after the first 90 days post-RT and up to 5 years post-RT.
- *Reconstruction failure* (up to 5 years post XRT): loss of the tissue expander or implant with the inability to replace it resulting in no final reconstruction or conversion to autologous reconstruction or revised with the addition of autologous reconstruction.[27, 28]
- *Patient Reported Outcomes/Quality of life*: Elements of the Patient-Reported Outcomes Version of the Common Terminology Criteria for Adverse Events (PRO-CTCAE) will be used for patient self-reporting of toxicities. The Breast Cancer Treatment Outcomes Scale (BCTOS) will be used to measure patient reported functional status (pain, mobility). Other measures of fatigue, pain, and arm function are listed in the appendix.
- *Patient self-reported cosmetic outcomes*: the patient self-reported outcome will be assessed using a modified Harvard Cosmesis Scale and a modified BCTOS at baseline, 2 years, and 5 years.

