18.0 Records and Data Collection Procedures

18.1 Submission Timetable

Initial Material(s) -

CRF	Treatment (Compliance with Test Schedule Section 4.0)
Institutional Contacts	
Patient Eligibility	
Demographics	
On-Study	≤2 weeks after registration
On Study: Neoadjuvant Chemotherapy	
Surgery	
Pathology of Ipsilateral Breast	
Breast Reconstruction	
Adjuvant Therapy	
Adverse Events- Baseline	
Specimen Submission: Blood (Baseline)	
Specimen Submission: Tissue (Baseline)*	*6 months after accrual

CRF	Treatment (Compliance with Test Schedule Section 4.0)
Patient Status: Baseline	
Patient Assessment	
Off Treatment	Submit ≤2 weeks after registration if withdrawal/refusal occurs prior to beginning protocol therapy

Test Schedule Material(s)

CRF	End of Treatment	12 weeks post/Observation Phase ⁴	Event Monitoring ⁵
Radiation Therapy	X		
Post Mastectomy Therapy: Chest Wall	X		
Radiation Therapy: Regional Nodes	X		
Patient Assessment	X	X	
Specimen Submission: Blood (post rad tx)	X		
Adverse Events Solicited	X	X	
Adverse Events: Other	X ²	X ²	
Off Treatment	X ²	X ²	
Patient Status Form	X	X	X
Specimen Submission: Tissue (Recurrence)		X ²	
Consent Withdrawal	X ²	X ²	
Lost to Follow-up	X ²	X ²	
Breast/Chest Wall Radiotherapy Questionnaire ³	X	X	

1. Complete at each evaluation during Active Treatment (see Section 4.0).
2. When applicable
3. Survey will need to be entered manually if has not alternately been scanned or entered electronically
4. Active monitoring observation phase, post radiation (+/- 2 days), 12 weeks (+/- 4 weeks), 12 months (+/- 30 days), annually for 4 years (+/- 3 months, total 5 years follow-up). If patient progresses within observation, they will move to the event monitoring phase where they will be followed until 5 years of follow-up information has been completed from the end of treatment timepoint
5. If patient has a recurrence prior to being off radiation therapy for 5 years, continue to follow yearly.

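### Listed toxicities are graded at widely spaced visits with no look-back or onset date and fall outside the grade 3-4 submission rule, so transient non-serious events can be missed or put in the wrong period

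*Combined protocol and SAP*

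**What the plan says.** - **Section 10.4** sets out "Adverse events to be graded at each evaluation and pretreatment symptoms/conditions to be evaluated at baseline per the CTCAE v4.0 grading". The table lists eleven terms, among them radiation dermatitis, fibrosis, seroma, esophagitis, breast infection and pneumonitis. It does not say whether the grade is that of the visit day or the worst since the last visit, and it asks for no onset date.
- **Section 10.5** covers "the following AEs experienced by a patient and not specified in Section 10.4" and asks for "Grade 3 and 4 AEs regardless of attribution to the study treatment or procedure". It states no timing.
- **Section 10.3** has the study team complete a worksheet and log once an adverse event has been identified, and leaves the reporting that follows to the sponsor-investigator. The example fields include the date of occurrence, severity and date of resolution. Serious events go through the data capture system. Neither route excludes the 10.4 terms.
- **Section 4.0** schedules toxicity assessment on the last day of treatment, at "12 weeks (+/- 8 weeks) post-radiation", and at 12 and 24 months, each within 3 months either side. **Section 18.1, footnote 4** gives "12 weeks (+/- 4 weeks), 12 months (+/- 30 days), annually for 4 years".
- **Section 16.2** divides acute from late events at 90 days after radiotherapy, and its aims are to "characterize acute and late adverse events including grade ≥ 2 pneumonitis and reconstruction failure rate". **Sections 16.621 and 16.622** tabulate each patient's maximum grade per event type.
- **Section 16.72** suspends accrual, arm by arm, if 3 or more of the first 15 treated patients (later, 20% or more of all patients) have a grade 3+ event within 90 days that is at least possibly related. Acute dermatitis does not count.

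**The concern.** The analyses need interval data: any event that occurred, its highest grade, and the side of day 90 on which it fell. The collection instructions ask for a grade at a few widely spaced evaluations and do not say that the grade must cover the time in between. The one section that calls for grade 3 and 4 events as a class leaves out the toxicities most expected from the treatment. A grade 3 esophagitis or breast infection that needs no admission and resolves before the next visit may be recorded, or may not, depending on local practice.

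With acute dermatitis excluded, the other listed acute toxicities are among the main events that could trigger the stopping rule. Grade 2 pneumonitis, part of a named secondary endpoint, is below the grade threshold of 10.5 in any case.

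**Working it through.** **1. The plan's own figure.** Section 16.4 states 80% power at 5% vs 10% and 41% at 10% vs 10%, with 72 evaluable patients (36 per arm), a 10-point margin and one-sided 0.05. Enumerating two binomials of 36, with success when the normal-approximation upper 95% limit for p1 - p0 is below 10 points, gives 79.4% and 41.7%. The stated figures reproduce, and the same model is used in step 5. (Section 16.61 names a 90% limit. The 95% limit of 16.4 is used because it matches the stated power; the 90% limit gives 88.2% and 56.8%.)

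**2. Routes for an event arising between evaluations.**

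| Event | 10.4 | 10.5 | 10.3 |
|---|---|---|---|
| Unlisted, grade 3-4 | not listed | submitted | log if identified |
| Listed, grade 3-4, serious | next evaluation, look-back unstated | excluded | serious-event report |
| Listed, grade 3-4, non-serious | next evaluation, look-back unstated | excluded | log if identified |
| Listed, grade 2 | next evaluation, look-back unstated | outside by grade | log if identified |

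**3. Gaps and the 90-day line.** Windows from 4.0:

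- 12 weeks to 12 months: nominally about 9 months; at the extremes, week 4 to month 15, about 14 months.
- 12 to 24 months: nominally 12 months; at the extremes, month 9 to month 27, 18 months.
- 12-week visit under 4.0: 12 ± 8 weeks = weeks 4 to 20 = days 28 to 140.
- 12-week visit under 18.1: 12 ± 4 weeks = weeks 8 to 16 = days 56 to 112.

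Day 90 is week 12.9, inside both windows. A visit on day 28 leaves 90 - 28 = 62 days of the stopping-rule window with no further solicited grading before month 9 at the earliest. A visit on day 140 comes 50 days after the window has closed, and without an onset date the grade cannot be assigned to acute or late.

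**4. Stopping rule.** Let s be the share of qualifying events that is captured. The documents give no value, so s is an assumption. P(at least 3 of 15) is the upper tail of a binomial(15, s × p), where p is the true rate:

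| True rate p | s = 1 | s = 0.75 | s = 0.5 |
|---|---|---|---|
| 10% | 18.4% | 9.7% | 3.6% |
| 20% | 60.2% | 39.6% | 18.4% |
| 30% | 87.3% | 69.0% | 39.6% |

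For the later 20% rule, the observed rate averages 20% only when the true rate is 20%/s: 26.7% at s = 0.75 and 40% at s = 0.5.

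**5. Primary comparison.** Section 16.4 expects at most 1% grade 3+ late toxicity, 15% unplanned surgery in reconstructed patients, and reconstruction in about two thirds. Surgery contributes 2/3 × 15% = 10%, which is the assumed control rate. Late events contribute at most 36 × 0.01 = 0.36 per arm, with a chance of at least one of 1 - 0.99^36 = 30%.

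Probability of wrongly declaring non-inferiority when the true rates are 10% and 20%:

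| Where the excess lies | s = 1 | s = 0.9 | s = 0.75 | s = 0.5 |
|---|---|---|---|---|
| Surgery; late events 1% per arm | 5.5% | 5.5% | 5.5% | 5.5% |
| Late events 1% vs 11%; surgery 9% per arm | 5.5% | 7.0% | 9.8% | 17.1% |

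In the second row the observed rates are 9% + 1% × s and 9% + 11% × s.

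**The case against.** A reader might infer that listed toxicities are graded only as present on the visit day, and that 10.5 is a between-visit reporting route closed to them. The documents support neither. Section 10.4 is silent on look-back and 10.5 is silent on timing. Section 18.1 schedules the solicited form and the form for other events at the same time points, so 10.5 reads naturally as dividing terms between two forms, with listed terms collected at every grade. Section 4.0 includes a history at each of these visits. Section 16.2 defines events by occurrence in the interval, and the maximum-grade wording points towards a look-back. The 10.3 log takes any identified event, so it would be wrong to say that non-serious listed events have no route. The stopping rule applies at any time, and the study team may suspend accrual without its being crossed.

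All of this stands, and it reduces the point to a gap in the collection instructions. It does not close the gap. The analysis text states what is needed, but no form or section tells staff to ask for it, and the log works only for events that come to notice.

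It is also tempting to size the loss by event duration. Two gradings in the 640 days from day 90 to day 730 would catch an event lasting d days with probability 2d/640, or 3d/640 if the 12-week visit falls after day 90: 4% to 7% for 14 days and 9% to 14% for 30 days. Those figures assume visit-day grading, no history, no log and durations that the documents do not give. They also do not suit persistent effects such as fibrosis. They should not be used as estimates.

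**Conclusion.** The point holds as an under-specified collection rule. Transient non-serious events of listed types can be missed, or placed on the wrong side of day 90. The consequences fall on the 90-day stopping rule, the grade 2+ pneumonitis endpoint and the maximum-grade tables. For the stopping rule, losing a quarter to a half of events would cut the chance of reaching 3 of 15 at a true 20% rate from 60% to between 40% and 18%. Those capture shares are assumptions, and the true share could be close to 1 if sites already ask about the interval.

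A reader might infer that missed events materially tilt the primary comparison towards non-inferiority. At the planning rates they do not. Late grade 3+ events are expected in at most 1%, and surgery, adjudicated separately under 11.4, makes up nearly all of the endpoint. The tilt appears only if the experimental arm has a real excess of grade 3+ late events. In the third of patients without reconstruction such events are the whole endpoint, but at the planned rate they remain few.

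**What to change.** 1. In 10.4 and on the solicited adverse event form, record the worst grade since the previous evaluation and its onset date. Classify events as acute or late by onset date. This is the essential change, and the only one that helps grade 2 pneumonitis.
2. In 10.5, remove the exclusion of 10.4 terms for grade 3+ events, or state that listed grade 3+ events are submitted when identified and counted for the stopping rule. Say that each event is entered once, so that the two forms do not duplicate it.
3. Reconcile the 12-week and 12-month windows in 4.0 and 18.1, so that the solicited assessment, with its look-back, covers the whole 90-day period. Which window to keep is for the investigators to decide.

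The cost is protocol wording, two form fields, slightly more chart review and a somewhat higher event count. No visits are added, and the stopping thresholds and the primary analysis are unchanged.
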